6.4.2.1.1. Primary Efficacy Analysis

The primary efficacy analysis will be conducted using the Treatment Extension Analysis Set.

The number and percentage of subjects with:

- Reduction of X for DYS,
- Reduction of X for NMPP,
- Stable or decreased use of analgesics for EAP during bleeding days, during non-bleeding days, and overall,
- Reduction of X for DYS and stable or decreased use of analgesics for EAP,
- Reduction of X for NMPP and stable or decreased use of analgesics for EAP,

will be presented.

There may be missing data during the screening period and whilst under treatment, for example, missed days of completing the eDiary. The primary analyses will use observed data only in such cases, provided that a minimum number of completed daily eDiary entries are available. This effectively assumes that the individual values such as daily eDiary assessments (observed or not) are independent of being missing. Subjects who have less than the minimum number of days available will be excluded from the analysis. This is valid under the assumption that such data is MAR, conditional on the baseline value.

The required minimum number of completed daily eDiary entries will be set to 12 days of each 28-day period (two Baseline menstrual cycles and the 28-day period prior to Month 12), i.e., 43% of non-missing assessments for the primary analysis, consistent with the use of 3 days per week as the minimum number of completed diary entries as suggested in recent research ((Griffiths & al, 2018), (Cappelleri & Bushmakin, Biopharmaceutical Report, 2020), (Cappelleri & Bushmakin, Biopharmaceutical Report, 2021)). The analysis will be repeated using subjects with at least 75% (21 days) and 35% (10 days) of completed daily eDiaries for DYS, NMPP and analgesic use.

The primary efficacy analysis will be repeated on the Per Protocol Extension Analysis Set.

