13.2 SAMPLE SIZE

With 150 subjects per each of the three treatment groups in the main study (450 subjects in total), the power was greater than 95% to reject the null hypothesis for both co-primary endpoints and 85% to reject all the null hypothesis for the ranked secondary endpoints. All subjects who have completed the full 6-month Treatment Period in the main study and who meet the inclusion criteria will be offered to enter the extension study. It is estimated that up to 288 subjects will enter the extension study, assuming that 80% of the patients randomized in the main study will complete the study (namely 360 subjects) and that up to 80 % thereof will enter the extension study.

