13.5 DATA ANALYSIS

The primary objective of this extension study is to assess the maintenance of efficacy of linzagolix administered orally once daily for up to an additional 6 months (for up to 12 months of treatment in total) in the subset of subjects who are treated with linzagolix up to the time point of interest. As such, the focus will be on subjects who received active treatment in the main study. The assessment of subjects who switched from placebo in the main study to active treatment in the extension study will be conducted as a secondary objective.

Subjects will be analyzed according to actual treatment received. The following four treatment groups will be analyzed: linzagolix 75 mg and linzagolix 200 mg with ABT fixed dose groups, linzagolix 75 mg and linzagolix 200 mg with ABT after 6 months placebo treatment. Only subjects with assessments at both baseline and the given time points will be included in the summaries. Baseline values are the same as in the main study (18-OBE2109-003 - Edelweiss 3), i.e. data collected prior to the treatment administration in the main study.

More details of the proposed statistical analyses will be described in the SAP, which will be written following finalization of the protocol and prior to database lock.

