1.2. Objectives

The primary objective of this extension study was to assess the maintenance of efficacy of linzagolix administered orally once daily for up to an additional 6 months (for up to 12 months of treatment in total) in women who had already completed 6 months of linzagolix treatment at a dose of 75 mg alone or of 200 mg in combination with add-back therapy (estradiol (E2) 1 mg / norethisterone acetate (NETA) 0.5 mg) in the management of moderate to severe endometriosis-associated pain (EAP) in women with surgically confirmed endometriosis. The two co-primary efficacy endpoints were clinically meaningful reduction over the last 28 days of randomized treatment up to the Month 12 visit, along with a stable or decreased use of analgesics for EAP, for 1) dysmenorrhea (DYS) and for 2) non menstrual pelvic pain (NMPP).

Secondary objectives included evaluation of efficacy over the last 28 days of randomized treatment up to the Month 12 visit based on the following parameters: evaluation of pain associated with sexual intercourse (dyspareunia) and defecation (dyschezia), difficulty of doing daily activities, analgesic use, assessment of subject perception of severity, change in uterine bleeding, Quality of Life (QoL) questionnaires, pharmacoeconomic burden of endometriosis by assessing changes in patient productivity, assessment of endometriosis-related number of non-study health visits, number of days in hospital and type of medical procedures performed during the Treatment Period.

Safety and tolerability objectives included assessment of bone mineral density (BMD), endometrial health, cardiac safety including QT interval prolongation, standard laboratory safety parameters, gynecological assessments and adverse event (AE) frequency including specific hypoestrogenic AEs.

Exploratory objectives included assessment of bone turnover markers and collection of pharmacokinetic (PK) and pharmacodynamic (PD) related data of linzagolix for a separate modelling exercise.

Populations for analysis, data handling rules, statistical methods, and formats for data presentation are provided. The statistical analyses and summary tabulations described in this SAP will provide the basis for the results sections of the clinical study report (CSR) for this trial.

This SAP will also outline any differences in the currently planned analytical objectives relative to those planned in the study protocol.

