6.2. General Statistical Methods

6.2.1. **General Methods**

All output will be incorporated into Microsoft Excel or Word files, sorted and labeled according to the International Conference on Harmonisation (ICH) recommendations, and formatted to the appropriate page size(s).

Tabulations will be produced for appropriate demographic, baseline, efficacy, pharmacokinetic and safety parameters.

The analyses will be performed on 4 treatment groups (taking into account the treatment taken in the main study):

- linzagolix 75 mg / linzagolix 75 mg
- linzagolix 200 mg with ABT / linzagolix 200 mg with ABT
- Placebo / linzagolix 75 mg (subject receiving placebo in main study and treated with linzagolix 75 mg in extension study)
- Placebo / linzagolix 200 mg with ABT (subject receiving placebo in main study and treated with linzagolix 200 mg with ABT in extension study)

For continuous data and for ordered categorical data, if appropriate, the number of non-missing observations, mean, standard deviation, median, first and third quartiles, minimum and maximum will be calculated, including for change from baseline when applicable.

The baseline mean will be calculated for all subjects based on the Extension Safety Analysis Set

For efficacy endpoints and BMD, a baseline mean will also be calculated for each visit using the baseline data for the subset of subjects who attended that visit, such that the same subjects contribute to the mean for the visit and the mean for the corresponding baseline values. Summary

CRS-BS-TP-000005 V 2.0

statistics will be based primarily on non-missing values. For ordered categorical data and nominal data, absolute counts and relative frequencies (in %) will be calculated.

Raw and derived data will be listed.

6.2.2. **Definition of Baseline**

The baseline will be described in two ways:

- Main Baseline (named Baseline), defined in the Statistical Analysis Plan of the main study and calculated according to first dose of IMP taken during the main Study.
- Second Baseline (named Baseline 2), defined as the last assessment before the first active dose of IMP during the extension study. For efficacy endpoints based on daily diary data, the Baseline 2 will be based on the last 28 days prior to and including last treatment administration in main study.

The baseline 2 will be calculated only for the subjects who are in the placebo arm (actual arm) in the main study.

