6.2.4. Multiple Comparisons/Multiplicity

No formal hypothesis tests are planned for this extension study. Data will be summarized by timepoint for each treatment group.

6.2.5. **Subgroups**

Not Applicable

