6.6.2. Bone Mineral Density (BMD) by DXA

BMD of femoral neck, total hip and lumbar spine will be assessed by DXA at Baseline, Month 9 (if required) Month 12 and Month 6 of the extension follow-up (if required). Unacceptable DXA assessments (accepted="No") will not be summarized (hip, spine and femur considered separately).

In case of repeated values due to BMD loss ≥5%, the initial scan will be used in summaries. Initial and repeated scan values will be reported in the listings.

Calibrated values will be used if available, otherwise initial values will be considered.

BMD, expressed as both absolute values and Z-scores will be summarized at each visit in terms of actual values, changes from baseline, changes from baseline 2 (only for the subjects who are

in the placebo arm in the main study) for each anatomic location. For absolute values only, percent change from baseline, percent changes from baseline 2 (only for the subjects who are in the placebo arm in the main study) and 95% confidence interval for the mean percent change from baseline and for the mean percent change from baseline 2 within each group will be produced at each time point.

The definition of both baselines are described in section 6.2.2.

Percent change from baseline and percent change from baseline 2 to Month 9, Month 12 and Month 6 extension follow-up will be described and will also be summarized in categories of percentage with the following classes:

- No change or increase,
- Decrease $\leq 3\%$,
- Decrease > 3% and $\leq 5\%$,
- Decrease > 5% and \leq 7%,
- Decrease > 7% and \leq 8%,
- Decrease > 8%.

All data except unacceptable DXA measurements (accepted="No") will be listed.

Due to the war situation in Ukraine, data from subjects in Ukraine sites may be incomplete, missing or uncleaned. A sensitivity analysis of the BMD will be performed, excluding data collected after 24FEB2022 for subjects from Ukraine sites. An additional listing including subjects from Ukraine only will be provided.

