6.6.8.5. Time to the first post-treatment menses

The first post-treatment menses will be defined from the Vaginal Bleeding daily ediary, as the first day for which the subject recorded bleeding after the last treatment administration date of the extension study, i.e., the first day with "BLEEDING" or "HEAVY BLEEDING" after the last treatment administration date of the extension study.

Time to first post-treatment menses is defined as:

Time to first post-treatment menses (days) = (day of first post-treatment menses – last treatment administration date in extension) + 1

Only data from the follow-up extension period will be included, and the analysis will be provided on the Follow-up Extension Safety Analysis Set, by treatment group.

Subjects who have not recorded any bleeding up to the end of the follow-up extension period will be considered as right-censored data at the last ediary vaginal bleeding record date before the end of the extension follow-up period (as defined in section 5.2) with time of censoring = last non-missing ediary vaginal bleeding record date – last treatment administration date in extension +1.

The probability of subjects having bleeding will be displayed by treatment group in the form of cumulative probability curves estimated using the non-parametric Kaplan-Meier method. Point estimates and corresponding 2-sided 95% CIs using the Greenwood's variance estimate will be provided at 28 days, 56 days, 84 days, 112 days, 140 days, 168 days, 196 days after the last treatment administration date in extension. Percentiles (25th, 50th, and 75th) and corresponding 2-sided 95% CIs will also be provided; "N/A" will be presented for any of the percentiles not reached.

Subjects with or without first post-treatment menses, time to first post-treatment menses, end of study status and end of study date will be presented in a by-subject listing.

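### The objective is maintenance from Month 6 to Month 12, but for the two continuing arms the plan has no within-subject Month 6 to Month 12 estimate and no confidence interval on the co-primary responder rates

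*SAP*

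**What the plan says.** SAP section 1.2 gives the objective as to "assess the maintenance of efficacy of linzagolix administered orally once daily for up to an additional 6 months", in women who have already had six months of linzagolix. Protocol section 13.5 adds that "the focus will be on subjects who received active treatment in the main study".

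The primary display, in SAP section 6.4.2.1.1, is "The number and percentage of subjects with" each pain reduction, stable or decreased analgesic use, and the two combined. The general rule in SAP section 6.2.1 matches: "For ordered categorical data and nominal data, absolute counts and relative frequencies (in %) will be calculated". The diary-completeness repeats, the per-protocol repeat and the Ukraine sensitivity analysis (6.4.2.2) all repeat this analysis. SAP section 6.2.4 states that "No formal hypothesis tests are planned for this extension study".

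Response is measured from the main-study, pre-treatment baseline (SAP 6.4.2.1). A second baseline taken before extension dosing exists, but SAP section 6.2.2 restricts it to women who were on placebo in the main study.

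Three provisions bear on Month 6:

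- SAP section 6.4.3.7 analyses responder rates at the other scheduled visits in the same way as the primary endpoint.
- SAP section 6.4 says main-study data will be summarized.
- The change table in SAP section 7 (V3.0) adds assessments from before Month 6 to the efficacy tables.

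Intervals are planned elsewhere. Bone mineral density gets a "95% confidence interval for the mean percent change from baseline" (SAP 6.6.2). For time to first menses, "Point estimates and corresponding 2-sided 95% CIs using the Greenwood's variance estimate will be provided" (SAP 6.6.8.5).

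**The concern.** Maintenance asks whether women who were doing well at Month 6 are still doing well at Month 12. A percentage at each visit gives only the net result of gains and losses. It does not show how many Month 6 responders lost response, and that number is what a prescriber considering treatment beyond six months would want.

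The second baseline does not fill the gap. It serves the women who switched from placebo, for whom a change after Month 6 measures onset of effect.

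The missing intervals are a smaller matter. The absence of hypothesis tests does not explain them, because the same SAP plans 95% intervals for two safety outcomes under the same no-test rule. As written, the primary endpoints are reported with less information on precision than those two outcomes.

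**Working it through.** **Arm size.** Protocol section 13.2 and SAP sections 2.2 and 6.1 give 450 randomized, 80% completing and up to 80% of those entering. 450 × 0.80 = 360 and 360 × 0.80 = 288, which reproduces the plan's figure. The documents give no split by arm. Assuming equal roll-over, each continuing arm has 288 / 3 = 96 women. Since 288 is an upper figure, 96 is as well.

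**Responder rate.** The documents give none for the extension. I assume 40% to 90%, and use 67/96 = 69.8% as the worked case.

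**What equal group rates allow.** With 67 responders at both visits, losses must equal gains. There are 96 − 67 = 29 Month 6 non-responders, so gains, and therefore losses, can lie anywhere from 0 to 29. The planned percentages would be the same whether 0/67 (0%) or 29/67 (43%) of Month 6 responders lost response. With 10 losses and 10 gains the loss is 10/67 = 15%.

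**Paired difference, Month 12 minus Month 6.** With g gains and l losses among n women, d = (g − l)/n and SE = √[(g + l) − (g − l)²/n] / n. The interval is d ± 1.96 × SE. At n = 96, with assumed counts:

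| Gains | Losses | d (points) | 95% CI (points) |
|---|---|---|---|
| 5 | 5 | 0 | −6.5 to +6.5 |
| 10 | 10 | 0 | −9.1 to +9.1 |
| 5 | 14 | −9.4 | −18.1 to −0.7 |
| 10 | 19 | −9.4 | −20.2 to +1.5 |

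For the second row, SE = √20 / 96 = 0.0466 and 1.96 × 0.0466 = 0.091. The last two rows show the same pair of group rates (67/96 = 69.8%, then 58/96 = 60.4%) but different intervals. The visit-by-visit percentages cannot tell them apart.

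**Retention.** With 10 losses among 67 Month 6 responders, retention is 57/67 = 85.1%, Wilson 95% CI 74.7% to 91.7%.

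**Single rate.** The Wilson half-width is z√[p(1 − p)/n + z²/(4n²)] / (1 + z²/n). At n = 96 and p = 0.5 this is 1.96 × √(0.002604 + 0.000104) / 1.040 = 0.098, or 9.8 points. At 67/96 the interval is 60.0% to 78.1% (half-width 9.0). At 86/96, about 90%, the half-width is 6.2. With 80 women instead of 96, the range is 6.7 to 10.7 points.

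**The case against.** The strongest reply is that the extension is descriptive by design, its co-primary endpoints are defined as response from the pre-treatment baseline at Month 12, and the plan already shows that response at each visit. A responder proportion that persists against pre-treatment pain is a fair descriptive reading of maintenance. That stands: the documents do not define maintenance as a change from Month 6, so the paired estimate is an addition to the planned endpoint and does not replace it.

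A reader might infer that no Month 6 comparison of any kind is planned. SAP sections 6.4, 6.4.3.7 and 7 show otherwise, because the net difference between group rates can be read off. That look is unpaired, though. Inclusion depends on baseline and the visit concerned (Protocol 13.5) and on at least 12 diary days in each 28-day period (SAP 6.4.2.1.1), so the women counted at Month 6 and Month 12 need not be the same.

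A single-rate interval can be worked out by any reader from n and %, so its absence is mainly one of presentation. The paired result cannot be worked out from the planned tables. SAP section 6.2.1 does list raw and derived data, so someone holding the subject listings could rebuild it, but that is not a planned summary.

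A reader might also infer that the sample-size section offers nothing but main-study power ("the power was greater than 95% to reject the null hypothesis for both co-primary endpoints"). It also gives the expected headcount, up to 288. The supportable point is that no precision is stated for that number.

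Finally, no arm stays on placebo after Month 6. A paired interval therefore addresses sampling noise only and cannot separate waning drug effect from disease course.

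**Conclusion.** The point holds in this form: for the two continuing arms, neither document plans a within-subject Month 6 to Month 12 change or a retention rate, and the co-primary responder percentages carry no interval. Month 6 and Month 12 group rates will be visible, but they do not identify loss of response. In the worked case they are compatible with a loss anywhere from 0% to 43% of Month 6 responders.

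Under the assumptions shown (96 per arm, equal roll-over, assumed gains and losses), the paired estimate would carry about ±6.5 to ±9.1 points when gains and losses balance. A single rate would carry about ±6 to ±10 points for rates of 40% to 90%. These are different quantities: single-rate half-widths should not be read as the precision of a fall between visits, which depends on how many women change status. The data and the endpoint definition are unaffected; what is incomplete is the summary that answers the stated objective.

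**What to change.** For the linzagolix 75 mg and linzagolix 200 mg with ABT continuing arms, add a Month 6 by Month 12 responder shift table, separately for DYS and NMPP. Use the responder thresholds already named in SAP section 6.4.2.1, the same thresholds at both visits, and only women evaluable at both visits. Report with it:

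- the paired difference, Month 12 minus Month 6, with a 95% CI;
- the retention rate among Month 6 responders, with a 95% CI.

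State how women who stop treatment early are handled. Under the existing primary rule their Month 12 value is the last 28 days on treatment, which overlaps the Month 6 window for anyone stopping within four weeks of Month 6.

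Add 95% Wilson or exact intervals to the co-primary responder percentages, and state the expected precision beside the figure of 288.

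Both visits' data are already in the planned analysis. The cost is a few table rows, with no hypothesis test and no new data. If the tables are already final, these can be issued as labelled supplementary outputs.

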6.4.2.2. Sensitivity analysis

Due to the war situation in Ukraine, data from subjects in Ukraine sites may be incomplete, missing or uncleaned. A sensitivity analysis of the primary endpoint analysis will be performed, excluding data collected after 24FEB2022 for subjects from Ukraine sites. An additional listing including subjects from Ukraine only will be provided.

6.4.3. Secondary/other/exploratory analysis

All secondary efficacy endpoints will be summarized by descriptive statistics for each treatment group, for each time point, including summaries of change from baseline when applicable.

Values for all endpoints that are collected daily using the eDiary (from Section 6.4.3.1 to Section 6.4.3.24) will be based on the 28 calendar days immediately prior to and including the day of the corresponding visit or prior to and including the last treatment administration date for Month 12, or the 28 calendar days immediately prior to and including the last dose date for subjects who discontinue treatment prior to the visit in question (or fewer if treatment is stopped less than 4 weeks after first dose date), in order to estimate the treatment effect while under treatment. The last 28 days on treatment will be used at all subsequent scheduled visits for those discontinued subjects. Descriptive summaries for each 28-day period will be performed in two ways however:

- Once including only values of 28 days prior to Month X, i.e. using the last 28 days prior to Month X eCRF visit date for subjects who have not discontinued up to that month. If subjects discontinued prior to Month X the corresponding value will be missing from the summary at Month X;
- Once applying the while on treatment strategy, i.e. using the last 28 days prior to Month X eCRF visit date for subjects who have not discontinued up to that month, and for subjects who discontinued prior to Month X, the last 28 days prior to treatment discontinuation will be used. For all subsequent timepoints (Month X+1, etc.) the same last 28 days prior to treatment discontinuation will be used.

Corresponding baseline values will be calculated based on the two baseline menstrual cycles, which may not be exactly 28 days each.

The values for other endpoints (monthly and 3-monthly questionnaires from Section 6.4.3.25 to Section 6.4.3.32) are defined as the value at the corresponding visit or value falling into the corresponding visit window as described in section 5.5. For these other endpoints, descriptive summaries by visit will be performed in two ways, once including values at the corresponding visit or value falling into the corresponding visit window as described in section 5.5, and once applying the while on treatment strategy, i.e., including values from the discontinued visits at each next scheduled visit.

For endpoints based on daily ediary data, analyses will use observed data only in such cases, provided that a minimum number of 43% (at least 12 days of each 28-day period) completed daily eDiary entries are available. Subjects who have less than the minimum number of days available will be excluded from the analysis. This is valid under the assumption that such data is MAR, conditional on the baseline value.

6.4.3.1. Change from baseline to Month 12 in DYS (VRS) and in NMPP (VRS)

Mean pelvic pain scores for DYS and for NMPP for each subject will be calculated in the same way as for the primary endpoints. The change from baseline to Month 12 (the last 28 days of randomized treatment up to the Month 12 visit, will be defined as the last 28 days prior to and including the last treatment administration date as defined in Section 5.2.1, or the 28 calendar days immediately prior to and including the last dose date for subjects who discontinue treatment prior to Month 12) in DYS using the VRS, and the change from baseline to Month 12 (the last 28

days of randomized treatment up to the Month 12 visit, will be defined as the last 28 days prior to and including last treatment administration date as defined in Section 5.2.1 or the 28 calendar days immediately prior to and including the last dose date for subjects who discontinue treatment prior to Month 12) in NMPP using the VRS.The mean pelvic pain scores for DYS and NMPP and change from baseline will be descriptively summarized. Summary will be repeated on the Per Protocol Extension Analysis Set.

Cumulative distribution functions (CDF) for change from baseline at Month 12 for DYS and NMPP will be provided, with separate lines for each treatment group. The x-axis will present the different values for the DYS or NMPP change from baseline, and the y-axis will present the proportion of subjects reaching each value of change. Vertical lines of the relevant responder thresholds will be displayed on the plots.

6.4.3.2. Change from baseline to Month 12 in dyschezia (Numeric Rating Scale - NRS)

Mean dyschezia scores for each subject will be calculated by averaging over the corresponding 28 calendar days immediately prior to and including the day of the last treatment administration as defined in Section 5.2.1 (or the 28 calendar days immediately prior to and including the last dose date for subjects who discontinue treatment prior to Month 12). The baseline mean dyschezia score will be calculated by averaging scores over the two baseline menstrual cycles. The mean dyschezia score and change from baseline will be descriptively summarized. Summary will be repeated on the Per Protocol Extension Analysis Set.

The number and percentage of subjects with a reduction of 1.5 from baseline to Month 12 for dyschezia will be presented. The reduction will be defined in a similar way as for the primary endpoint but using dyschezia scores at the Month 12 timepoint.

